### Data analysis plan

Exploratory data analysis will be conducted to examine the distributions of all outcome measurements, demographic and clinical factors. Detection of outliers will be done using histograms, box-plots, normal plots and summary statistics. We will conduct the Kolmogorov-Smirnov or the Shapiro-Wilk test to confirm normality of variables. Where deviated from normality, we will do the suitable transformations such as a box-cox transformation to approximate normality for the subsequent analyses. Missing data will be imputed when appropriate. The Statistical Package for Social Sciences version 17.0 (SPSS Inc, Chicago, IL) will be used for all statistical analysis.

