# **Data Analysis**

### Sample Size Justification

There are no previous studies with exact means in ODI for a BMAC group not the association between clinical outcomes and concentration of MSCs and CFUs. Therefore, assumptions had to be made. If the standard deviation for each group was assumed to be 10 and equivalence as within 12.8 (MCID), given 90% power and alpha=0.05, we would need 14 patients per group. However, if we assume equivalence as within 6 points, we would need 59 patients per group. We understand that assumptions greatly affect sample size, and therefore, our desired sample size of 60 patients is appropriate.

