# Aim 1: Clinical Study

This study will analyze the clinical and radiographic outcomes in terms of pre-operative measures, intra-operative measures, and post-operative measures followed-up for in the three groups.

Primary Outcome Endpoint: As per the primary outcome measure, fusion status at 1 year will be assessed via CT scan by an independent radiologist. Clinical outcomes will be defined by patient reported and health-related quality of life measures previously defined. Differences from preoperative visit to post-operative time points will be compared between the 3 groups by Student t-tests. Based on preliminary data, improvements are expected in these outcome measures: ODI from 33.42 (SD:6.22) to 26.75 (SD:8.19); SF-12 PCS from 29.00 (SD:6.05) to 31.42 (SD:6.05); SF-12 MCS from 31.42 (SD: 6.50) to 35.75 (SD: 13.82); NRS from 8.17 (SD: 1.27) to 5.93 (SD: 1.90). Multivariate regression analysis, controlling for age, sex, race, and charlson comorbidity index, will be performed to determine the effect of treatment on reaching MCID values, as defined in Parker et al 2012.[2]

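### The test-then-transform rule reaches the ODI and other HRQOL change scores, where ordinary Box-Cox needs an unspecified shift and the result would no longer be in points

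*Combined protocol and SAP*

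**What the plan says.** The section Data analysis plan covers all outcome measurements together with demographic and clinical factors. It sets a pre-test, "We will conduct the Kolmogorov-Smirnov or the Shapiro-Wilk test to confirm normality of variables", and then a consequence: "Where deviated from normality, we will do the suitable transformations such as a box-cox transformation to approximate normality for the subsequent analyses". It does not say which of the two tests decides or at what level. It gives no rule for choosing the Box-Cox parameter, no shift for non-positive values, no back-transformation and no rank-based or robust alternative.

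Aim 1: Clinical Study gives the analysis of the patient-reported outcomes: "Differences from preoperative visit to post-operative time points will be compared between the 3 groups by Student t-tests". The same section gives expected values from preliminary data, among them "ODI from 33.42 (SD:6.22) to 26.75 (SD:8.19"). It also plans a regression on reaching MCID values and names CT fusion status at 1 year as the primary outcome.

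Sample Size Justification is the only place where similarity on the ODI is given a size. It uses an SD of 10 with margins of 12.8 points (the MCID) or 6 points.

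**The concern.** The variables that Aim 1 compares are differences from baseline. Some patients do not improve, so these differences include zeros and negative values. The one transformation that the plan names is defined only for positive data. An analyst who follows the text must therefore choose a shift, or a different transformation, after seeing the data.

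The trial's hypothesis is that the arms are similar, and on the ODI that can only be judged in points. A t-test on non-linearly transformed changes gives a p-value and a difference in units that cannot be set against 12.8 or 6 points. The pre-test is also run on the data being analysed. With five follow-up visits and about 17 completers per arm, one outcome could be reported in points at one visit and in transformed units at another.

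**Working it through.** **The plan's own figure.** For equivalence of two means with true difference 0, SD 10, alpha 0.05 per side and 90% power, n per group = 2 × [10 × (1.645 + 1.645) / margin]².
- Margin 12.8: 13.2, so 14. This matches "given 90% power and alpha=0.05, we would need 14 patients per group".
- Margin 6: 60.1, so 61, against 59 stated. The two-sided normal formula with 1.960 + 1.282 gives 59 at margin 6, and 13 at margin 12.8.

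The stated sizes are thus reproduced to within two patients. They are calculated in ODI points, and the transformation rule does not enter them.

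**Share of ODI changes that are not positive.** Inputs from Aim 1: pre-operative mean 33.42 (SD 6.22), post-operative mean 26.75 (SD 8.19). Mean improvement = 33.42 − 26.75 = 6.67. The pre-post correlation r and the shape of the changes are not given. I assume normal changes and vary r.

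SD of change = √(6.22² + 8.19² − 2 × r × 6.22 × 8.19) = √(105.76 − 101.88 r). Share with improvement ≤ 0 = Φ(−6.67 / SD of change).

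| r | SD of change | Improvement ≤ 0 | Post minus pre ≤ 0 |
|---|---|---|---|
| 0 | 10.28 | 26% | 74% |
| 0.3 | 8.67 | 22% | 78% |
| 0.5 | 7.40 | 18% | 82% |
| 0.7 | 5.87 | 13% | 87% |
| 0.8 | 4.93 | 9% | 91% |

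The plan does not fix the sign of the change, so both are shown. Even with the favourable sign and r = 0.8, the chance that all 51 expected completers (3 × 17) improve is (1 − 0.088)⁵¹, about 0.9%. It is smaller at every lower r.

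The same formula on the other Aim 1 figures, for r from 0.7 to 0.3, gives non-positive improvement in 30–37% for SF-12 PCS, 34–37% for SF-12 MCS and 5–12% for NRS.

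**Does the named method run?** On simulated changes of this kind (mean 6.67, SD 8, n = 51), the standard one-parameter Box-Cox routine stopped because the data must be positive. After a constant was added it ran, and so did the Yeo-Johnson transformation.

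**Loss of the points scale.** The effect is easiest to see on raw scores. On the log scale (Box-Cox parameter 0), a 12.8-point difference starting from a score of 10 is ln(22.8/10) = 0.82. Starting from 40 it is ln(52.8/40) = 0.28. At parameter 0.5 the same two differences are 3.2 and 1.9 units. Only parameter 1, which is no transformation beyond a constant, keeps 12.8 points at one value.

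**The case against.** The strongest reply is that the step is conditional and Box-Cox is only an example. A transformation undefined for the data is not a suitable one, and shifted or extended versions do run. If normality is not rejected, the t-test is done on changes in ODI points, as Aim 1 describes. The shares above also assume normal changes, and under that model a 5% test would reject only about 5% of the time. They therefore do not show how often the rule would bite, or any bias, error rate or changed conclusion. All of this stands. A reader might infer that the ODI comparison cannot be computed at all, and the documents do not support that. What remains is that the choice of shift, transformation and scale is left open until the data are seen.

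A second reply is that the 12.8-point margin appears only in the sample size text. No equivalence test or confidence interval against it is planned, so a reader who infers that the rule would spoil a planned margin test goes too far. This also stands: the missing equivalence analysis is a separate and larger gap, and removing the transformation does not close it. But that gap can be closed only with an estimate in points, and the present rule can take that estimate away.

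Finally, the normality paragraph does not name ODI change. The link comes from reading it with Aim 1, and it is a fair link because nothing is exempted.

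**Conclusion.** The concern holds as a defect of specification and of scale, not as an impossibility. If the rule is triggered for ODI change, ordinary Box-Cox needs a shift that the plan does not give, since about 13% to 22% of improvements would be zero or negative for r from 0.7 to 0.3, and 9% to 26% for r from 0.8 to 0. These shares rest on the Aim 1 means and SDs, whose time point is not stated, and on the assumed correlation and normal shape. That some changes will be non-positive does not depend on the value of r chosen. Any non-linear transformation gives a result that cannot be read in ODI points, and the scale may vary between visits according to a pre-test on the same data.

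The rule does not affect the CT fusion primary outcome, the stated 14 or 59 per group, or MCID responder status, which can be derived from raw scores. The matter is therefore of moderate weight. It should be corrected before analysis, but it does not undermine the primary comparison.

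**What to change.** For ODI and the other HRQOL outcomes, remove the normality pre-test and the transformation that follows from it. State instead that each will be analysed in its own points with a linear model containing treatment arm and the baseline score, and that between-arm differences will be reported with robust or bootstrap confidence intervals. Add a rank-based test as a sensitivity analysis. Fix the sign of the change so that improvement is unambiguous.

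Keep transformation for measures that are strictly positive, such as laboratory counts in Aim 2 and blood loss, and name those measures and the transformation in advance.

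Baseline adjustment is not strictly needed to cure the transformation problem. It is recommended because the baseline scores are already collected and the model replaces the separate t-tests on change. The cost is one rewritten paragraph and a small amount of extra analysis work, with no new data and no change to the sample size. The resulting intervals in points would also be what a later-specified equivalence analysis against the margin needs.

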### • Arthodesis rate one year post-operation (paired t-test):

The effect size (ES) in this study was 0.4, considered to be low using Cohen's (1988) criteria. With an alpha = .05 and power = 0.80, the projected sample size needed with this effect size is approximately N = 23.

Thus, our proposed sample size of N=60 (with 20 patients per arm; effectively 40 for t-tests between groups) will be more than adequate for the main objective of this study and should also allow for expected attrition

Completion rate of enrolled patients in our protocol is estimated to be 85% based on standard clinical follow up rates for lumbar Spinal Fusion patients at the investigators practices. Therefore, by enrolling 20, we expect at least 17 in each group.

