### Randomization Process

The process of randomization will be computerized and completed by an individual not associated with the study. The randomization will be performed at 1:1:1 ratio between the three arms. Sequenced and sealed envelopes or a similar randomization technology approach will be used. Given posterior, anterior and anterior-posterior surgical techniques will be randomly included in the three study arms, we anticipate equal stratification. However, if study arms show predominance to one surgical approach, attempt will be made to increase enrollment of patients of the unbalanced surgical approach.

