# **Process of Consent: Subject Capacity & Subject Comprehension**

Potential participants will be asked to review a copy of the informed consent form prior to enrollment. The investigators will use an informed consent form that has been approved by the Institutional Review Board (IRB) at this institution. Patients will be recruited when meeting all inclusion and exclusion criteria. Once recruited, all subjects will go through the informed consent process. One or more of the research team members will explain, in simple terms, the details about the outcome collection and the subject's involvement.

Patients must have the capacity to comprehend and give informed consent. Patient will be given the opportunity to ask questions prior to signing the informed consent (ICF). Comprehension of

PI: [name]

the study will be tested by asking the subject and his/her family follow-up questions about their understanding of the study procedures and follow-up process after informed consent has been given. During this time frame and throughout the time period of the study, the research team will re-educate the patient on the study. Additionally, this will provide the patients with the opportunity to make a fully informed decision about their participation in the outcomes data collection, prior to signing the ICF. This will ensure that all subjects understand the nature of the outcomes data collection, the risks and benefits involved, and their commitment to complete all follow-up visits.

Health information will be collected from participants who are a part of this research study. By signing the consent form, participants will allow the primary investigator and researchers to use health information, but only to use it within this research. Information will only be used as explained in the consent form or when required by law.

Patient participation will require 7 visits as per routine care: 1 screening visit (15 minutes to determine if patient is qualified for study), 1 pre-operative visit (1-2 hrs to gather preliminary information), and 5 follow up visits at 6 weeks, 3 months, 6 months, 12 months, and 24 months (each requiring about 1 hour per visit).

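### HRQOL change scores go to Student t-tests with no stated imputation method or pooling rule; a baseline-adjusted repeated-measures model would close that gap and be more precise

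*Combined protocol and SAP*

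**What the plan says.** The missing-data rule, under Data analysis plan, is "Missing data will be imputed when appropriate". It gives no method, predictors, missingness assumption, pooling rule or sensitivity analysis, and it is not limited to HRQOL. For the CT endpoint there is one further rule: under Costs to the Subject, patients who refuse the scan leave the primary analysis and stay in the secondary one.

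For HRQOL, Aim 1 states: "Differences from preoperative visit to post-operative time points will be compared between the 3 groups by Student t-tests". The only other model there is "Multivariate regression analysis, controlling for age, sex, race, and charlson comorbidity index, will be performed", which concerns reaching the minimal clinically important difference and is not described as a repeated-measures analysis.

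Each HRQOL score is collected before surgery and, under Process of Consent, at "5 follow up visits at 6 weeks, 3 months, 6 months, 12 months, and 24 months". Expected loss is given under Sample Size Analysis: "Completion rate of enrolled patients in our protocol is estimated to be 85"%, so that "by enrolling 20, we expect at least 17 in each group". That completion rate is not tied to a visit.

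**The concern.** An ordinary t-test treats every value it receives as observed. If missing scores are filled in once and the completed data are tested, the filled values add degrees of freedom without adding information. With mean or regression filling they also shrink the spread. The standard error is then too small and differences between arms are declared too often. The text neither requires nor excludes this route, and the words on appropriateness leave the decision until the data can be seen.

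The second issue does not depend on imputation. Subtracting the baseline removes the right amount of between-patient variation only when baseline and follow-up are very highly correlated. Otherwise, adjusting for baseline as a covariate gives a smaller standard error from the same patients. With about 17 completers per arm that precision matters, because the hypothesis of similar outcomes is set at 24 months and rests partly on these scores.

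**Working it through.** **Inputs from the protocol.** 20 patients per arm, 1:1:1; 85% completion; SD 10 for ODI (Sample Size Justification); baseline plus five visits. The protocol's own figure reproduces: 20 × 0.85 = 17 per arm.

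**Assumptions not in the protocol.** Within-patient correlation 0.3 to 0.7, equal between all visits; the 3 losses per arm fall at 24 months, completely at random; no true difference; one pair of arms at nominal two-sided 5%.

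**Step 1: arm-mean filling, closed form.** Each filled value equals the arm mean, so the sum of squares stays the same while the divisors grow. With m = 17 observed and n = 20 analysed:

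- SE ratio to complete cases = √[m(m−1) / (n(n−1))] = √[(17 × 16) / (20 × 19)] = √(272/380) = 0.846, so the SE is 15% too small.
- The t-test uses 38 degrees of freedom (critical value 2.024) where 32 are real (2.037). CI width ratio = 0.846 × 2.024 / 2.037 = 0.841, about 16% too narrow.
- Type I error = P(|t₃₂| > 0.846 × 2.024 = 1.713) = 9.6%. With 2 of 20 missing it is 7.8%; with 4 of 20, 11.8%. No correlation enters this step.

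**Step 2: other routes the sentence allows, by simulation.** 6,000 runs per correlation for the imputation routes and 2,500 for the repeated-measures model; ranges are over correlations 0.3, 0.5 and 0.7.

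| Handling of missing 24-month scores | Reported SE / true SD | Type I error |
|---|---|---|
| Arm mean, then t-test | 0.83–0.84 | 9.3–9.9% |
| Deterministic regression, then t-test | 0.88–0.89 | 7.9–8.6% |
| One random regression draw, then t-test | 0.89–0.90 | 7.2–7.9% |
| Last score carried forward, then t-test | 0.99–1.00 | 4.8–5.2% |
| Multiple imputation, 20 sets, Rubin's rules | 1.01–1.03 | 3.8–4.3% |
| Repeated-measures model, no imputation | 0.99–1.00 | 4.6–5.0% |

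**Step 3: precision at 24 months.** For 17 completers per arm, the SE of a difference in change is 10 × √[2(1−ρ)] × √(2/17). Adjusting for baseline instead gives approximately 10 × √(1−ρ²) × √(2/17). The ratio is √[(1+ρ)/2] = 0.81, 0.87 and 0.92 at ρ = 0.3, 0.5 and 0.7. Simulated SEs agree:

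| Analysis | ρ = 0.3 | ρ = 0.5 | ρ = 0.7 |
|---|---|---|---|
| Completers, t-test on change | 4.01 | 3.40 | 2.64 |
| Completers, adjusted for baseline only | 3.30 | 3.00 | 2.47 |
| Repeated-measures model, baseline-adjusted, five visits | 3.28 | 2.96 | 2.43 |

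From first row to last: 3.28/4.01 = 0.82, 2.96/3.40 = 0.87 and 2.43/2.64 = 0.92, a fall of 8 to 18%. From second row to last: 3.28/3.30 = 0.99, 2.96/3.00 = 0.99 and 2.43/2.47 = 0.98, so the extra visits add only about 1 to 2%.

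**The case against.** The strongest reply is that silence about a method is not a choice of the worst one. That stands. A reader might infer that the error bars will come out too narrow, but the sentence permits multiple imputation, or no imputation at all, and neither produces that fault. Carrying the last score forward also held 5%, though only because the simulation assumed flat scores lost at random. Aim 1 expects ODI to improve from 33.42 to 26.75, so the risk with that method is bias.

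A reader might also infer that narrow intervals would produce false claims of equivalence at a calculable rate. The documents do not support such a rate. The 12.8-point margin appears only in the sample-size justification, the hypothesis says only that outcomes will be similar, and the planned tests are tests of difference.

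A third tempting reading is that the five visits themselves deliver the precision gain. Step 3 shows that nearly all of it comes from baseline adjustment, which completers alone would also give.

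Two further limits stand. The 15% loss is an overall figure, stated beneath a one-year arthrodesis calculation, and placing it at 24 months is an assumption. The repeated-measures model was tested on data that matched its covariance structure, which favours it. These points reduce how firmly the error can be stated. They do not fill the gap in the plan or make the t-test on change efficient.

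**Conclusion.** The concern holds in a conditional form. The plan does not say how missing HRQOL scores are imputed or how that uncertainty reaches the t-tests. If single filling by arm mean or regression were used with 17 of 20 observed per arm, type I error would be about 7 to 10% instead of 5%. The arm-mean figure of 9.6% needs only that completion count and normal, randomly missing data; the others rest on correlations of 0.3 to 0.7. Multiple imputation with pooling would not have the problem.

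The inefficiency of the t-test on change applies whatever is done about missing data. Under the same assumptions, a baseline-adjusted repeated-measures model lowers the 24-month SE by 8 to 18% and keeps type I error near 5%.

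This concerns the HRQOL scores and not the CT fusion endpoint. It should be corrected, but it does not undermine the primary analysis.

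**What to change.** For HRQOL scores, replace both the t-tests on change and the imputation sentence with the following:

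- Analyse each score by one mixed model for repeated measures on all observed post-operative visits, with arm, visit, arm-by-visit, baseline and baseline-by-visit terms.
- State the covariance structure, a fallback if the model does not converge, and the degrees-of-freedom method.
- Report 24-month differences between arms with confidence intervals from this model.
- State a rule for missing baseline scores, which the model does not resolve by itself; treating baseline as a further response is one option. PROMIS is optional in this study, so such gaps are foreseeable.
- Bar single imputation. Any imputation is multiple imputation with pooled standard errors, as a sensitivity analysis.

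The cost is SAP wording and slightly more analysis work, with no new data. The model is a little harder to explain than a t-test and assumes that missingness depends only on observed data.

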# Aim 1: Clinical Study

This study will analyze the clinical and radiographic outcomes in terms of pre-operative measures, intra-operative measures, and post-operative measures followed-up for in the three groups.

Primary Outcome Endpoint: As per the primary outcome measure, fusion status at 1 year will be assessed via CT scan by an independent radiologist. Clinical outcomes will be defined by patient reported and health-related quality of life measures previously defined. Differences from preoperative visit to post-operative time points will be compared between the 3 groups by Student t-tests. Based on preliminary data, improvements are expected in these outcome measures: ODI from 33.42 (SD:6.22) to 26.75 (SD:8.19); SF-12 PCS from 29.00 (SD:6.05) to 31.42 (SD:6.05); SF-12 MCS from 31.42 (SD: 6.50) to 35.75 (SD: 13.82); NRS from 8.17 (SD: 1.27) to 5.93 (SD: 1.90). Multivariate regression analysis, controlling for age, sex, race, and charlson comorbidity index, will be performed to determine the effect of treatment on reaching MCID values, as defined in Parker et al 2012.[2]

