## Conclusions of previous clinical models

BMP has been used since 2002 in the lumbar spine to promote bony fusion since its approval by the FDA for use in anterior lumbar interbody fusion, and is now approved for use in posterior and transforaminal approaches. BMP augment bony growth is promoting MSC and osteoprogenitor cell differentiation into osteoblasts, which is very similar to BMAC. In a 2015 systematic review of lumbar fusion rates with the use of rhBMP-2, Galimberti et al showed interbody lumbar fusion rates ranging from 97.8-93.6%. However, as detailed in a review of randomized clinic trials by Chrastil et al in 2013, despite high fusion rates, there may complications associated with BMP such as heterotopic ossification, radiculitis, and endplate osteolysis. While usage of BMP is attractive for avoiding autologous grafting—decreasing operative times, blood loss, avoiding donor site morbidity, and allowing for biologics in older, more morbid patients that may have a limited autograft supply.

Previous reports by Connolly et al., Gangji et al., Hernigou et al., and Gessmann et al. have also shown that high concentrations of adult stem cells from iliac crest bone marrow can enhance the rate and amount of bone formation. The authors report that technology that quickly and easily concentrates bone marrow stem cells 3 to 6 times harvested baseline concentrations makes practical the use of adult bone marrow stem cells in a spinal fusion. In a study by Gan et al., they found a 95% successful spinal fusion rate when 252 mL BMA harvested from the iliac crest was

PI: [name]

concentrated peri-operatively down to 45 mL enriched suspension. In contrast, the historical autograft fusion success rate ranges between 65-95%.

These studies conclude that both BMP and BMAC mimic and supplement the body's natural response to trauma by stimulating vasculogenesis and tissue regeneration. BMAC contains many cell types, while BMP contains only one, the question of superiority between the two methods of bone healing/remodeling stimulation is unanswered. As BMAC is autologous, there are no immuno-rejection side-effects or concerns regarding disease transmission.

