### Preliminary Data

In an earlier study with unpublished results, 14 BMAC+allograft patients were compared to 3 ICBG. This randomized series determined radiographic fusion in 92.9% of cases among the BMAC+allograft and ICBG cohorts, suggesting no difference in fusion efficacy among these grafts. This study did not identify any difference between lumbar spinal fusion patients receiving ICBG versus BMAC+allograft during surgery, on the basis of patient-reported outcomes up to 1-year follow-up and fusion grading. Only higher SF-12 MCS scores at baseline among ICBG patients were sustained at 6-weeks and 6-months post-operative. These preliminary results are important given the controversy surrounding effective use of interbody grafts, but are not decisive especially when, for many surgeons, the choice is between BMP and BMAC.

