# Our hypothesis is that:

For patients who undergo lumbar spinal fusion surgery with interbody support, the outcomes in terms of pre-operative measures, intra-operative measures, and post-operative measures in the investigational group (BMAC + allograft) will be similar to the compared BMP group and control group at 24 months postoperatively.

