# **Research Design & Methods**

Subjects who are candidates for lumbar spinal fusion with interbody support will be screened for inclusion in the study. All procedures are approved by the FDA (see appendix A for approved labeling) and are common practice at NYULMC. If the subject meets all of the eligibility criteria

PI: [name]

and agrees to participate in the study after informed consent, they will be enrolled into one of the three arms.

An enrollment ratio of BMAC + allograft to BMP to Autograft with bone marrow aspirate (control) (1:1:1) for a total of 60 subjects to be enrolled in the study. The study will determine and compare differences in fusion rate and health related quality of life parameters at 6 weeks, 3 months, 6 months, 1 year, and 2 years postoperatively.

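### The plan hypothesises similarity, but Aim 1 contains only difference analyses, names no between-arm analysis of 1-year CT fusion, and drops patients who refuse the CT

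*Combined protocol and SAP*

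**What the plan says.** - **Hypothesis (Our hypothesis is that).** Outcomes "in the investigational group (BMAC + allograft) will be similar to the compared BMP group and control group at 24 months postoperatively".
- **Primary endpoint (Aim 1: Clinical Study).** "As per the primary outcome measure, fusion status at 1 year will be assessed via CT scan by an independent radiologist". The text then moves to patient-reported outcomes.
- **Aim 1 analyses.** "Differences from preoperative visit to post-operative time points will be compared between the 3 groups by Student t-tests". In addition, a multivariate regression "will be performed to determine the effect of treatment on reaching MCID values".
- **Data analysis plan.** Covers distributions, normality checks, transformation and software, and says only that imputation will be used where appropriate. It names no analysis of fusion.
- **Sample Size Justification.** Sizes ODI on equivalence with SD 10, 90% power and alpha 0.05: 14 per group for a margin of 12.8 (the MCID), 59 per group for a margin of 6. It chooses neither margin.
- **Sample Size Analysis.** Labels the 1-year arthrodesis calculation a paired t-test and mentions t-tests between groups; 20 per arm are enrolled and at least 17 are expected to complete.
- **Costs to the Subject.** Patients may refuse the 1-year CT; they are then left out of the primary analysis but kept in the secondary one.

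**The concern.** A difference test that fails to reject does not show similarity. To support the stated hypothesis, the plan needs a margin and a rule that compares a confidence interval with it, or else it needs to present the comparison as estimation. Aim 1 does neither. For the primary endpoint there is not even a named difference test: the t-tests concern change from the pre-operative visit, and fusion status has no such value.

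The risk is that a non-significant fusion result from a small trial is reported as similar fusion. Preliminary Data shows how easily this happens: a series of 14 versus 3 patients is described as "suggesting no difference in fusion efficacy among these grafts", although the same section adds that those results are not decisive.

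Two further gaps affect the same comparison. Refusing a CT is a choice made about a year after randomisation, so removing refusers can break the comparability of the arms. And the hypothesis is set at 24 months while the primary endpoint is at 1 year.

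**Working it through.** **Inputs.** 20 enrolled and 17 completing per arm (Sample Size Analysis). Fusion 94% for BMP-2 and 85% for bone marrow aspirate, not concentrate (Criteria for Action). Background says "the historical autograft fusion success rate ranges between 65-95"%, so 85% is also plausible for the control arm. ODI SD 10 and margins 12.8 and 6 (Sample Size Justification). ODI SDs 6.22 before and 8.19 after surgery (Aim 1). Fusion margins, the number of missing CTs and the pre-post correlation are my assumptions.

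**1. The plan's ODI figures.**
- Two one-sided tests (TOST), alpha 0.05, true difference 0: n = 2[SD(1.645 + 1.645)/margin]². Margin 12.8 gives 13.2, so 14; margin 6 gives 60.1, so 61.
- Two-sided 0.05 formula: n = 2[SD(1.96 + 1.282)/margin]². Margin 12.8 gives 12.8, so 13; margin 6 gives 58.4, so 59.

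The stated 14 and 59 are reproduced to within two patients either way, but neither formula gives both exactly. The section therefore does not settle the confidence level.

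**2. ODI equivalence at 17-20 per arm, SD 10.** Equivalence requires |difference| + t × 10 × √(2/n) < margin. For a 90% interval the half-width is 1.694 × 3.43 = 5.8 at 17 per arm and 1.686 × 3.16 = 5.3 at 20.

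| Interval | Margin 12.8 | Margin 6 |
|---|---|---|
| 90% | 96-98% | 10-18% |
| 95% | 90-95% | 1-4% |

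With the Aim 1 SDs, change SD = √(6.22² + 8.19² − 2ρ × 6.22 × 8.19) = 10.28, 8.67, 7.40 and 5.87 at ρ = 0, 0.3, 0.5 and 0.7. Power at margin 6 (90% interval) is then 7-15%, 26-39%, 50-62% and 80-87%.

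**3. Fusion: power of a difference test.** Summing Bin(a; n, 0.94) × Bin(b; n, 0.85) over all tables with p ≤ 0.05 gives, at 17 and 20 per arm, 0.038 and 0.058 (Fisher) or 0.099 and 0.130 (uncorrected chi-square).

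**4. Fusion: what an interval can show.** Miettinen-Nurminen score intervals with identical results in both arms:

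| Fused, each arm | 95% half-width | 90% half-width |
|---|---|---|
| 20/20 | 16.5 points | 12.2 points |
| 19/20 | 19.7 | 15.6 |
| 17/17 | 18.9 | 14.1 |
| 16/17 | 22.6 | 18.0 |

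20/20 in both arms is the most favourable outcome for two-sided equivalence, and both its limits exceed 10 points. Two-sided equivalence within 10 points is therefore impossible at this size.

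One-sided non-inferiority is different. A result of 20/20 versus 18/20 has a lower 95% limit of −7.3 points. By exact enumeration, with equal true rates of 85% or 94% and 17 or 20 per arm, the chance of meeting the margin is:

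| Assumed margin | 95% interval | 90% interval |
|---|---|---|
| 10 points | 0.101-0.126 | 0.185-0.257 |
| 15 points | 0.185-0.257 | 0.298-0.456 |

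**5. Missing CTs (assumed 3 of 20 per arm).** Observed 17/17 versus 17/17 is a difference of 0. If all missing CTs in one arm are fused and none in the other, it becomes 20/20 − 17/20 = 15 points. Observed 17/17 versus 14/17 is 17.6 points; with the opposite assignment it becomes 17/20 − 17/20 = 0, a shift of 17.6.

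**The case against.** The strongest reply is that this is a small study that does contain equivalence margins and does signal a fusion test. Several parts of that stand.

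- It would be wrong to infer that the document has no margin anywhere. Sample Size Justification has two, for ODI; they are sample-size alternatives and are not carried into Aim 1. Only 12.8 fits 20 per arm, so the ODI repair is mainly a matter of stating the rule.
- It would be wrong to infer that no fusion test is mentioned. Sample Size Analysis mentions t-tests, but only in sizing text, and pairing does not fit three independent arms.
- A reader might infer that no result could meet a 10-point fusion margin. That is true only of two-sided equivalence. The hypothesis does not state sidedness, and the 10% reduction in Criteria for Action is one-sided and is a stopping rule, not an analysis margin.
- A reader might infer that the aims conflict, because Research Design & Methods says "The study will determine and compare differences in fusion rate and health related quality of life parameters" and the background says "the question of superiority between the two methods of bone healing/remodeling stimulation is unanswered". The documents do not support this: equivalence is itself judged on a difference, and the second remark is literature background.
- The CT-refusal rule is stated in advance and keeps refusers in the secondary analysis, and no refusal rate is given. That limits what can be said about the size of any bias, but does not remove the post-randomisation exclusion, and the general remark on imputation does not say how these patients are handled.

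None of this supplies a between-arm analysis of the primary endpoint or a rule for concluding similarity.

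**Conclusion.** The plan is wrong as written on this point. Its hypothesis is similarity, its Aim 1 analyses test differences, and its primary endpoint has no named between-arm analysis. These findings rest on the text alone.

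The consequence depends on size. At 17-20 per arm a non-significant fusion comparison is the expected result even with a 9-point deficit, so it carries almost no evidence of similarity. The 9 points come from the plan's own quoted rates, with the caveat that 85% is for aspirate rather than concentrate. The 10- and 15-point fusion margins and the three missing CTs per arm are illustrations, not figures from the plan.

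For ODI the weakness is confined to the 6-point margin, where power depends heavily on the SD and correlation assumed (7% to 87%). It should not be read as saying that the trial cannot show ODI equivalence, nor that the plan's own figures fix a 90% interval.

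**What to change.** 1. **Fusion.** Report the risk difference with a score-based interval for BMAC versus BMP and BMAC versus control, and restate the fusion aim as estimation. State that a non-significant difference will not be read as similarity. State also that 17-20 per arm cannot show two-sided equivalence within 10 points and has only about a 10-26% chance of showing one-sided non-inferiority at 10 points. If a similarity claim is kept, justify and fix the margin, its sidedness and the confidence level before outcomes are seen, and report any other result as inconclusive.
2. **ODI.** Choose one of the two margins and one time point in advance, judge equivalence by the interval, and state the confidence level and the power.
3. **Missing CT.** Do not rely on the exclusion alone. Beside the observed-CT result, present all randomised and operated patients with best- and worst-case bounds, and draw a conclusion only if it holds across them.
4. **Time point.** Reconcile the 24-month hypothesis with the 1-year primary endpoint.

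The cost is analysis-plan wording and modest programming, with no new data or enrolment. The price to the sponsor is a less favourable stated conclusion on fusion.
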